8.3.1 Criteria and guidelines for non-reportable events

Except as otherwise noted in the CIP, the following events are not reportable to the sponsor:

- Unavoidable events, as listed in Table 2 that resolve within the timeframes specified

8.3.2 Criteria and guidelines for reportable events

Records relating to the subject's subsequent medical course must be maintained and submitted (as applicable) to the Sponsor until the event has subsided or, in case of permanent impairment, until the event stabilizes and the overall clinical outcome has been ascertained. Adverse events will be monitored until they are adequately resolved. The status of the subject's condition should be documented at each visit.

The investigator will report the event to the IRB per their reporting requirements.

Clinical Investigational Plan

Reportable events to sponsor are considered:

- ADEs, SADEs, and UADEs caused by or associated with the MRI scan (except unavoidable events related to the MRI scan)
- Unavoidable ADEs whose conditions worsen or continue beyond the time frame listed in the Unavoidable events tables.
- All ADEs and SADEs that are not associated with the MRI scan

All above events will be reported to the Sponsor, as soon as possible, but no later than 10 days of first learning of the event. A list of foreseeable adverse events and anticipated adverse device effects include, but are not limited to, those listed in Table 1. Refer to section 3.3 for full details.

The Sponsor will ensure that all adverse events are reported to the relevant authorities as per regulations. The description of the adverse event, date of the adverse event, treatment and resolution of the reportable adverse events will be reported, as applicable, to the relevant authorities per regulations. Additional information may be requested, when required, by the Sponsor in order to support the reporting of AE CRFs to regulatory authorities.

The investigator must notify the IRB, if appropriate, in accordance with national and local laws and regulations, of the AE CRFs reported to the Sponsor.

8.4 Subject Death

8.4.1 Procedure for recording and reporting subject death

All subject deaths are to be documented and reported to the sponsor within 10 working days after becoming aware of the event.

The Clinical Events Committee (CEC) (see section 14.1) reviewing adverse device effects noted in sections 8.1.2-8.3.1 for the study will also review and classify all potential subject deaths. All subject deaths that occur during this investigation must be reported to St. Jude Medical as soon as possible. Notification of death should include a detailed statement of the pertinent events and be signed by the investigator in addition to the appropriate case report forms (Death CRF, Withdrawal CRF, and Product Out of Service CRF). It is the investigator's responsibility to notify the IRB per the IRB policy. Details of death and the following information, if available, should be provided in a letter to St. Jude Medical by the investigator summarizing the subject's course since enrollment in the study:

- Date and time of death
- Place death occurred (e.g. hospital, nursing home, subject's home)
- If death was witnessed
- Identification of the rhythm at the time of death, if known (include any available documentation)

Clinical Investigational Plan

- Cause of death
- Any other circumstances surrounding the death
- Approximate time interval to death from the initiating event.
- Autopsy report (if performed)
- Whether it was device and/or procedure related
- Whether it was related to the study
- Device configuration at the time of death

If any of the above information is not available, provide an explanation in the death narrative of what attempts (and how many) were made to obtain the information, and the outcome of those attempts. At a minimum, two (2) phone calls should be placed, followed by a certified letter, to the subject's next of kin. Provide clinical notes and witness statements. If possible, interrogate the ICD. Retrieve and print all episode diagnostics, IEGMs, and programmed parameters.

Every attempt should be made to explant the device and/or leads intact. Any explanted SJM devices or leads should be returned to St. Jude Medical for analysis promptly. In the event that the device is not explanted, the above procedure must be followed to retrieve the data. The reason the device and/or lead(s) are not being returned to St. Jude Medical must be stated clearly on the case report form.

8.5 Complaint

A complaint is defined as an inadequacy of a medical device with respect to its identity, quality, durability, reliability, safety or performance. Complaints may be submitted from the time of consent through the end of the study.

If a complaint involves an adverse device effect category or death as described in the protocol (section 8.1-8.4), then the investigator shall notify the Sponsor by completing the adverse event or death case report form as applicable and must provide the Sponsor with all necessary documentation needed.

If the complaint does not involve a reportable adverse event per protocol the investigator should notify the SJM Product Surveillance Department through one of the methods listed below as soon as possible after becoming aware of a complaint.

Complaints will be collected and reported by St. Jude Medical according to our product reporting process.

Clinical Investigational Plan

9.0 Data Management

Overall, the Sponsor will be responsible for the data handling. The sponsor and/or its affiliates will be responsible for compiling and submitting all required reports to governmental agencies.

Data will be analyzed by the Sponsor and may be transferred to the Sponsor's locations outside of the US and/or any other worldwide regulatory authority in support of a market-approval application.

St. Jude Medical respects and protects personally identifiable information that we collect or maintain. The privacy of each subject and confidentiality of his/her information will be preserved in reports and when publishing any data. Confidentiality of data will be observed by all parties involved at all times throughout the clinical study. All data will be secured against unauthorized access.

An electronic data capture (EDC) system will be used to collect data and store data specified in the CIP. This data collection includes all data points found on the electronic case report forms (eCRFs) for the study. The EDC system may also be used to upload source documents related, but not limited to AE CRFs and deaths.

The Principal Investigator or institution will provide direct access to source data during and after the clinical study for monitoring, audits, IRB review and regulatory authority inspections. As required, the Principal Investigator or institution will obtain permission for direct access to source documents from the subject, hospital administration and national regulatory authorities before starting the clinical study.

9.1 Data Management Plan

A detailed Data Management Plan (DMP) will be established to ensure consistency of data collection. This document will include procedures used for data review, database cleaning, and issuing and resolving data queries. If appropriate, the DMP may be updated throughout the study duration. All revisions will be tracked and document controlled.

CRF data will be captured in a validated electronic database management Oracle Clinical system hosted by St. Jude Medical. Only authorized site personnel will be permitted to enter the data through the electronic data capture (EDC) system deployed by St. Jude Medical. An electronic audit trail will be used to track any subsequent changes of the entered data.

Clinical Investigational Plan

9.2 Document and Data Control

9.2.1 Traceability of documents and data

The investigator will ensure accuracy, completeness, legibility and timeliness of the data reported to the sponsor on the CRFs and in all required reports.

9.2.2 Recording Data

Source documents will be created and maintained by the investigational site team throughout the clinical study.

The data reported on the CRFs will be derived from, and be consistent with, these source documents, and any discrepancies will be explained in writing.

All data reported for the study must be substantiated with source documentation in the subject's medical records, clinic records or other forms of documentation provided by or approved by Sponsor.

The CRFs will be validated (eCRF) by the authorized site personnel.

10.0 Monitoring

It is the responsibility of St. Jude Medical as the sponsor of the study to ensure the study is conducted, recorded, and reported according to the approved protocol, subsequent amendment(s), applicable regulations, and guidance documents. Monitoring will be conducted according to the St. Jude Medical Clinical Monitoring standard operating procedure.

Prior to beginning the study, St. Jude Medical will contact the investigator or designee to discuss the study and data requirements. A St. Jude Medical monitor will periodically review the subject records and associated source documents.

The investigator shall make subject and study records available to the clinical monitor for monitoring.

11.0 Regulatory Inspections

The investigator and/or delegate should contact St. Jude Medical immediately upon notification of a governmental agency inspection at the site. A clinical monitor or designee will assist the investigator and/or delegate in preparing for the audit.

An investigator who has authority to grant access will permit authorized governmental agency employees, at reasonable times and in reasonable manner, to enter and inspect any

Clinical Investigational Plan

establishment where devices are held (including any establishment where devices are used or where records or results are kept).

An investigator, or any person acting on behalf of such a person with respect to the study, will permit authorized governmental agency employees, at reasonable times and in reasonable manner, to inspect and copy all records relating to the study.

An investigator will permit authorized governmental agency employees to inspect and copy records that identify subjects, upon notice that governmental agency has reason to suspect that adequate informed consent was not obtained, or that reports required to be submitted by the investigator, to the Sponsor or IRB have not been submitted or are incomplete, inaccurate, false or misleading.

12.0 Statistical considerations

The following section presents statistical considerations for the study. The primary objective of this study is to characterize the image quality, clinical impact, and diagnostic utility of MRI in patients undergoing clinically indicated, non-thoracic 1.5T MRI scans who are implanted with a St. Jude Medical pacemaker, ICD, or CRT device.

12.1 Statistical design, hypotheses, method and analytical procedures

12.1.1 Primary endpoint#1:

The proportion of MRI scans from pacemakers or CRT-Ps providing sufficient quality to allow for a diagnostic interpretation.

The primary endpoint will be reported as the number of MRI scans providing sufficient quality to allow for a diagnostic interpretation divided by total number of MRI scans along with the 95% lower confidence bound (LCB) calculated using Clopper-Pearson exact method.

12.1.2 Primary endpoint#2:

The proportion of MRI scans from ICDs or CRT-Ds providing sufficient quality to allow for a diagnostic interpretation.

The primary endpoint will be reported as the number of MRI scans providing sufficient quality to allow for a diagnostic interpretation divided by total number of MRI scans along with the 95% lower confidence bound (LCB) calculated using Clopper-Pearson exact method.

Clinical Investigational Plan

12.1.3 Additional Data:

- Demographics: gender, age, ethnicity, race, cardiac disease history, arrhythmia history, etc.
- A summary of scan location (i.e. head, extremity, lumbar)
- A summary of clinical findings based on review of MRI scans
- A summary of device electrical measurements at the MRI Scan Visit (before and immediately after the MRI scan) and at subsequent Follow-up Visit(s).
- A summary of adverse events (ADE, SADE, UADE)
- A summary of MRI-related complications
- Mortality
- Estimate of the incidence rate of device patients undergoing a clinically indicated MRI scan.

The above data will be summarized by each main device group (pacemaker/CRT-P and ICD/CRT-D).

12.2 Sample size

Assuming 95% of the MRI scans are of sufficient quality to allow for a diagnostic interpretation, a sample size of 150 MRI scans for each of the two main device groups (Pacemaker/CRT-P and ICD/CRT-D) provides a 95% confidence interval half-width of 4.0%.

For each of the 2 main device groups, a minimum of 25 head scans, 25 extremity scans, and 25 lumbar scans will be collected, with the remainder of scans to be from any of these 3 scan regions in order to ensure an adequate distribution of these different scan regions.

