4.2.1 Number of Subjects Required to be Included in the Study

The maximum number of subjects in the study is 300 from 2 main device groups (150 subjects with a pacemaker/CRT-P and 150 subjects with an ICD/CRT-D. A maximum of 45 subject enrollments will be allowed per center (15% of total subjects enrolled). For each of the 2 main device groups, a minimum of 25 head scans, 25 extremity scans, and 25 lumbar scans will be collected with the remainder of scans to be from any of these 3 scan regions.

Clinical Investigational Plan

A patient will be considered enrolled in the study after he/she meets the inclusion/exclusion criteria, signs an IRB-approved informed consent form, and the subject's device is programmed to enter the MRI environment.

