12.3 Pass/fail criteria to be applied to the results of the clinical study

No pass/fail criterion is applied to the results of the clinical study.

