12.8 The treatment of missing, unused or spurious data, including drop-outs and withdrawals

There are no plans to perform imputations for missing data, subject dropouts or withdrawals. If spurious data are discovered, these data will be excluded from analyses. Reasons for exclusion of any data from analyses will be summarized.

12.9 The exclusion of particular information for the testing of the hypothesis, if relevant

There is no hypothesis for this study.

12.10 In multi-center studies, the minimum and maximum number of subjects to be included for each center

A minimum of 1 subject and a maximum of 45 subjects may be included at each center enrolling in the study.

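### Does the 4.0% half-width in section 12.2 misstate the precision of a primary analysis that reports only a lower confidence bound?

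*Combined protocol and SAP*

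**What the plan says.** Section 12.2 begins "Assuming 95% of the MRI scans are of sufficient quality to allow for a diagnostic interpretation". On that basis it takes "a sample size of 150 MRI scans for each of the two main device groups" and states that this "provides a 95% confidence interval half-width of 4.0" percent. It names no interval method and does not say whether the interval is one- or two-sided.

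Sections 12.1.1 and 12.1.2 define the two primary results, one for pacemakers and CRT-Ps and one for ICDs and CRT-Ds. Each is the count of adequate scans over all scans, "along with the 95% lower confidence bound (LCB) calculated using Clopper-Pearson exact method". No upper limit is planned, and the tail area of the bound (5% or 2.5%) is not given.

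Three further provisions set the context:

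- Section 12.3: "No pass/fail criterion is applied to the results of the clinical study".
- Section 12.9: "There is no hypothesis for this study".
- Section 4.2.1: "The maximum number of subjects in the study is 300 from 2 main device groups", that is, 150 per group. Under section 4.6.2 a subject counts as enrolled once the device is programmed for the scan, and under section 12.7 only subjects who complete the scan enter the primary analysis.

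**The concern.** The sample-size section and the analysis section describe different quantities. A half-width belongs to an interval with two limits, whereas the analysis reports one limit. The number itself also raises suspicion. At exactly 95% of 150, the distance from the estimate to the one-sided 95% Clopper-Pearson bound is 4.00 points, while the two-sided exact half-width is 3.85, the Wilson half-width 3.62 and the Wald half-width 3.49. It is natural to infer that a one-sided distance was given a two-sided label.

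If so, the only quantitative justification for the sample size would be wrong. A reader subtracting 4.0 from 95 would expect a lower limit of 91.0%, when the lower limit of the two-sided 95% interval is 90.2%. In addition, the figure is computed at 150 scans, enrolment is capped at 150 per group, and only completed scans are analysed. Any non-completion would then seem to erode the stated precision.

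**Working it through.** **Inputs.** Assumed proportion 0.95 and n = 150 per group (section 12.2); Clopper-Pearson method (section 12.1). Since 0.95 × 150 = 142.5 is not a possible count, the neighbouring counts 142 and 143 are shown beside it.

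**Formulas.** With x adequate scans out of n:

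- lower limit = Beta quantile at q with parameters (x, n − x + 1);
- upper limit = Beta quantile at 1 − q with parameters (x + 1, n − x);
- q = 0.025 for a two-sided 95% interval, q = 0.05 for a one-sided 95% bound;
- half-width = (upper − lower) / 2.

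**Step 1: the plan's own figure, n = 150.**

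| x | Estimate | Two-sided 95% interval | Half-width | Below / above estimate | One-sided 95% bound | Distance to that bound |
|---|---|---|---|---|---|---|
| 142 | 94.67% | 89.76% to 97.67% | 3.95 | 4.90 / 3.00 | 90.58% | 4.08 |
| 142.5 | 95.00% | 90.19% to 97.89% | 3.85 | 4.81 / 2.89 | 91.00% | 4.00 |
| 143 | 95.33% | 90.62% to 98.10% | 3.74 | 4.71 / 2.77 | 91.41% | 3.92 |

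At 142 the half-width is (97.670 − 89.762) / 2 = 3.954, which rounds to 4.0. The stated figure is therefore reproduced as an ordinary two-sided exact half-width at a whole count, by the method that section 12.1 names. The one-sided distance gives 4.00 only at the fractional count; at whole counts it rounds to 4.1 or 3.9. The numbers cannot show that a one-sided distance was used, and they do not show the stated figure to be wrong.

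**Step 2: dependence on 150 completed scans.** The documents give no non-completion rate. Assume 140 analysed scans per group, a loss of 10/150 = 6.7%. At 133/140 = 95.0% the two-sided interval is 89.97% to 97.97%, with half-width 3.998, which still rounds to 4.0. The distance to the one-sided bound is 4.19, and to the two-sided lower limit 5.03.

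**Step 3: size of the ambiguity in the lower bound.** One-sided 95% bound minus two-sided lower limit, n = 150:

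- x = 142: 90.58 − 89.76 = 0.82 points;
- x = 142.5: 91.00 − 90.19 = 0.81 points;
- x = 143: 91.41 − 90.62 = 0.79 points.

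**The case for a change.** The strongest case for a change does not need the 4.0% to be wrong. The planning sentence describes an interval while the analysis gives a single bound, and that bound has two readings about 0.8 points apart. At 142 of 150 the readings fall on opposite sides of 90% (90.58% and 89.76%), and a primary result should not leave its confidence level to be settled after the data are seen. A symmetric half-width also describes an asymmetric exact interval poorly. The side that will be reported lies 4.7 to 4.9 points below the estimate on the two-sided reading, not 4.0. Finally, a study meant to characterise image quality has no evident reason to omit the upper limit, and the remedy would cost only a few words.

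Most of this is accurate as description. The mismatch in wording and the missing tail probability are real. But 90% has no standing in the plan, so falling on one side of it or the other decides nothing. Section 12.2 states a half-width and promises no particular lower limit; reading 91.0% out of it assumes a symmetry that an exact interval does not have. The lower side is the informative one for a proportion of adequate scans. Because the numerator and denominator are reported, any reader can compute the upper limit or the other version of the lower one.

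**Conclusion.** The concern does not hold as an arithmetic error. The stated 4.0% agrees with the two-sided exact half-width at 142 of 150 (3.95 points) and at 133 of 140 (4.00 points), so it is neither shown to be wrong nor dependent on every enrolled subject completing the scan.

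What remains is a missing detail: whether the lower bound carries 5% or 2.5% in its tail. An analyst would ordinarily read an unqualified 95% lower confidence bound as one-sided, and would label it in the report. The other reading moves the bound by about 0.8 points. With no hypothesis, success criterion, interim look or statistical stopping rule (sections 12.3 to 12.5 and 12.9), that shift alters no decision, and the sample size would stay the same. Adding an upper limit is a reporting preference, and replacing a figure that reproduces would correct nothing.

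This conclusion rests on the plan's assumed 95% and on the Clopper-Pearson method of section 12.1 having been used for section 12.2, which that section does not say. The 140-scan case is an illustration, not a figure from the documents. If a performance threshold were ever attached to these endpoints, the sidedness would have to be fixed first; the present plan attaches none.

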12.3 Pass/fail criteria to be applied to the results of the clinical study

No pass/fail criterion is applied to the results of the clinical study.

12.4 The provision for an interim analysis

There are no planned interim analyses for the study

12.5 Criteria for the termination of the clinical study on statistical grounds

There is no planned termination for the study based on statistical grounds.

12.6 The specification of subgroups for analysis

There are no planned subgroup analyses for the study

Clinical Investigational Plan

12.7 Procedures that take into account all the data

Analyses of primary endpoint will be performed in subjects who complete the MRI scan. Subject accountability for enrolled subjects will be performed prior to analyses of the primary endpoint.

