4.4 Endpoints

4.4.1 Primary Endpoints

4.4.1.1 Primary Endpoint #1:

The proportion of MRI scans from pacemakers or CRT-Ps providing sufficient image quality to allow for a diagnostic interpretation.

4.4.1.2 Primary Endpoint #2:

The proportion of MRI scans from ICDs or CRT-Ds providing sufficient image quality to allow for a diagnostic interpretation.

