4.6.2 Point of Enrollment

Subjects are considered enrolled after the informed consent form has been signed (Refer to section 4.7 for the Informed Consent Process), it has been verified that the subject meets all of the inclusion and none of the exclusion criteria, and the subject's device is programmed to enter the MRI environment.

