6.3.1.1 Situations where subject does not meet eligibility criteria

If a subject does not meet all inclusion criteria or meets any of the exclusion criteria, the subject cannot participate in the study and cannot be enrolled. In case the subject was already consented to participate in the study, but does not meet inclusion/exclusion criteria, the following actions will be taken.

Issues where patient was consented, but did not meet inclusion/exclusion criteria	Action
If the subject's device was NOT programmed to enter the MRI environment and the MRI Scan did NOT take place (i.e. subject changed their mind about undergoing MRI scan)	
• Document enrollment information (name of the study, date of consent and inclusion/exclusion) in the subject's medical and/or study records• Complete the Enrollment CRF and Screen Failure/Withdrawal CRF. The subject is a screen failure.
If the subject's device WAS programmed to enter the MRI environment but the MRI Scan did NOT take place (i.e. subject changed their mind about undergoing the MRI scan):	
• Document enrollment information (name of the study, date of consent and inclusion/exclusion) and MRI Scan Visit information in the subject's medical and/or study records• Complete the Enrollment CRF• Complete the Deviation CRF for inclusion/exclusion criteria not met• Complete the Withdrawal CRF. The patient is withdrawn
If the subject's device WAS programmed to enter the MRI environment AND the MRI Scan has been performed:	
• Document enrollment information (name of the study, date of consent and inclusion/exclusion) and MRI Scan Visit information in the subject's medical and/or study records• Complete the Enrollment CRF• Complete the MRI Scan CRF• Complete the Deviation CRF for inclusion/exclusion criteria not met

Clinical Investigational Plan

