6.4.2 Cardiac Monitoring

- During the entire MRI scan, the subject's cardiac function must be monitored by a study trained electrophysiologist, cardiologist, or Advanced Cardiac Life Support (ACLS) trained personnel capable of delivering external cardiac pacing, defibrillation and advanced cardiac life support using an ECG and/or pulse oximetry along with the site's routine monitoring. In cases where ECG monitoring is not readily available, monitoring via pulse oximetry alone is considered acceptable. Routine monitoring of the subject must also take place

Clinical Investigational Plan

to assess and/or confirm any clinically significant changes noted in the subject's oxygen saturation or heart rate, as well as any clinically significant complaints not obvious with pulse oximetry. Record these changes and complaints during the MRI scan.

- ACLS procedures must be in place to address situations where a life threatening arrhythmia and/or hemodynamic collapse occurs. The programmer must be used outside the American College of Radiology (ACR) defined Zone 4 magnet room. If the subject's hemodynamic function is compromised during the MRI scan, discontinue the MRI procedure and take proper measures to restore the subject's hemodynamic function.

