6.4.4 Handling of Subjects Unable to Tolerate an MR Scan

In cases where the scan cannot be tolerated by the subject, remove the subject from the scanner. Assess the subject for possible adverse events, and treat the subject's reported symptoms according to your institution's standard of practice. Document the reason for the intolerance. At a minimum, information related to the sequence used to perform the scan, the length of time the subject was scanned, and the whole body SAR level reached should be collected and submitted to St. Jude Medical. A repeat scan is not required to be completed.

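### Does the undefined word *complete* in section 12.7 leave the primary analysis set unsettled for scans that were started and then stopped?

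*Combined protocol and SAP*

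**What the plan says.** Section 4.4.1 defines the endpoints over scans. For the first device group the endpoint is "The proportion of MRI scans from pacemakers or CRT-Ps providing sufficient image quality to allow for a diagnostic interpretation", and the second is the same for ICDs and CRT-Ds. Section 12.1 computes each as the number of sufficient scans "divided by total number of MRI scans along with the 95% lower confidence bound (LCB) calculated using Clopper-Pearson exact method".

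Section 12.7 then sets the population: "Analyses of primary endpoint will be performed in subjects who complete the MRI scan". Its next sentence reads "Subject accountability for enrolled subjects will be performed prior to analyses of the primary endpoint".

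Three other parts of the plan bear on how 12.7 is read:

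- **Enrolment (4.6.2).** A subject is enrolled after consent, confirmation of eligibility, "and the subject's device is programmed to enter the MRI environment". Enrolment therefore precedes the scan. The table in 6.3.1.1 has a row for a device that was "programmed to enter the MRI environment but the MRI Scan did NOT take place".
- **Stopped scans (6.4.2, 6.4.4).** If hemodynamic function is "compromised during the MRI scan, discontinue the MRI procedure". For a subject who cannot tolerate the scan, 6.4.4 asks for the reason and some scan details, and adds "A repeat scan is not required to be completed".
- **Image rating (6.5.3).** The radiologist rates image quality as sufficient or insufficient. Stopped scans are not excepted.

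Section 12.8 plans no imputation and promises a summary of the reasons for excluding data. Sections 12.3 and 12.9 state that there is no pass/fail criterion and no hypothesis.

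**The concern.** In ordinary usage, a scan abandoned halfway has not been completed. Read that way, 12.7 drops every started-then-stopped scan, whereas 12.1 taken alone keeps any scan that took place. A stopped scan may be the subject's only scan, because no repeat is required, and it may still carry a rating under 6.5.3. The plan does not say whether that rating enters the primary proportion.

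If stopped scans are less often diagnostic than completed ones, leaving them out gives a higher proportion and a higher lower confidence bound (LCB) than counting every started scan. These are the study's two primary results, so an ambiguous denominator deserves a check.

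**Working it through.** **1. The plan's own precision figure.** Section 12.2 assumes 95% sufficient and 150 scans per group, and states a half-width of 4.0%. The exact two-sided 95% Clopper-Pearson interval at 142/150 runs from 89.76% to 97.67%. Half its width is (97.67 − 89.76)/2 = 3.95 points, which agrees with the stated figure.

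**2. Size of the shift.** The plan gives no stop rate and no diagnostic share for stopped scans, so both are assumed. Take 150 started scans, k of them stopped, and 7 insufficient among the completed scans (about 95% sufficient, as in 12.2). The LCB is taken as the one-sided 95% exact bound.

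- Completed scans only: (143 − k)/(150 − k).
- All started scans, no stopped scan diagnostic: (143 − k)/150.
- Gap in general: (k/150) × (proportion sufficient among completed − proportion sufficient among stopped).

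| Stops k | Completed only (LCB) | All started, none of the stopped diagnostic (LCB) | Gap in proportion |
|---|---|---|---|
| 1 | 142/149 = 95.30% (91.36%) | 142/150 = 94.67% (90.58%) | 0.64 points |
| 3 | 140/147 = 95.24% (91.24%) | 140/150 = 93.33% (88.95%) | 1.90 points |
| 6 | 137/144 = 95.14% (91.06%) | 137/150 = 91.33% (86.57%) | 3.81 points |
| 7 | 136/143 = 95.10% (91.00%) | 136/150 = 90.67% (85.79%) | 4.44 points |
| 10 | 133/140 = 95.00% (90.81%) | 133/150 = 88.67% (83.49%) | 6.33 points |

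The last two columns are the worst case. If half of 10 stopped scans are diagnostic, the all-started figure is 138/150 = 92.00% (LCB 87.36%), a gap of 3.00 points. With half diagnostic, a 4.0-point gap needs 4.0/(95 − 50) = 8.9% of scans to stop. If every stopped scan is diagnostic, the all-started figure is 143/150 = 95.33% (LCB 91.41%), at most 0.33 points above the completed-scan figure.

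Precision hardly depends on the choice. With 10 stopped scans left out, the exact half-width at 133/140 is 4.00 points.

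**3. How the protocol uses the word.** Three other places speak of completing a scan:

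- Exclusion criterion 6 in 4.5.2 concerns another implant whose labeling would not allow the scans to be completed.
- Section 6.4 says that a radiology staff member completes the clinically indicated scan.
- Section 6.4.4 says of a second scan that "A repeat scan is not required to be completed".

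In each, *completed* means carried out. None refers to acquiring every planned sequence.

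**4. What 12.7 has to do.** Because enrolment occurs at programming, some enrolled subjects may have no scan at all. A scan-based proportion cannot include them, so a clause is needed to remove them, and the accountability sentence that follows concerns enrolled subjects. Read this way, the set in 12.7 and the denominator in 12.1 are the same. Every scan rated under 6.5.3 enters the proportion, and scans without a rating appear in accountability and in the summary of exclusion reasons.

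**The case for a change.** The best case for a change is that *complete* is neither *undergo* nor *start*, and that a primary analysis set should not depend on which reading the analyst picks. The protocol itself foresees stopped scans, 6.5.3 can give them a valid rating, and 12.8 reports exclusions without defining them. A definition, with the proportion shown over both all started and completed scans, would take a few sentences and one extra figure per device group.

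Part of this stands. The word is undefined in the readable text, and a one-sentence clarification would do no harm. The larger remedy does not follow, for three reasons:

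- The endpoint is image quality. A subject who leaves the scanner from claustrophobia, which Table 2 lists among events expected with any MRI scan, may have produced no image to judge. Counting that scan as insufficient mixes tolerance with image quality and acts as failure imputation, which 12.8 does not plan. Statisticians could reasonably differ on it.
- Defining completion as acquisition of all planned sequences needs planned and acquired sequences for every scan. The items listed in 6.5.3, an open list, include neither.
- If the planned summaries give counts of excluded scans, a reader can compute the worst case directly, as in the table above. The image ratings of excluded scans would not be recoverable that way.

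**Conclusion.** No change is needed. The gap is one undefined word, and the protocol's own usage and its point of enrolment favour a reading that matches 12.1. Leaving tolerance stops out of an image-quality proportion is also defensible. Following the plan gives a sound descriptive estimate under either treatment, and no test or decision rule depends on it.

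The effect is unknown and may be negligible. Under the assumptions above, 1 to 3 stops per 150 shift the proportion by at most 0.6 to 1.9 points. The shift passes the planned 4.0-point half-width only from 7 stops (7/150 = 4.7%) with none diagnostic, or from about 9% stops with half diagnostic.

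Confidence is moderate. The study flow chart (Figure 1) could not be read and the case report forms are under separate cover; either may show how a stopped scan is handled.
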